# 2.1. Table 1 - study overview of most recent RCTs evaluating nutritional therapy in medical inpatients

First author year	Patient type	N	Study intervention	Control treatment	Outcomes evaluated	Main effects of study Intervention	Limitations	Ref
Somanchi, 2011	Adult hospitalized medical patients	400	Individualized nutritional counseling	Standard nutritional care	LOS, diagnosis coding of malnutrition cases delays in nutritiona support	Significant reduction in LOS with economic benefit	No patient leve randomization	11
Starke J 2011	Malnourished general medica inpatients	132	Individualized ONS	Standard nutritional care	Caloric intake, weight vitamin levels, QoL complications, readmission, mortality (6m)	Higher caloric/proteir intake, less weight loss increased QoL, fewer complications	time-consuming	12
Rüfenacht U, 2010	Malnourished general medica inpatients	36	Intensive nutritional counseling with ONS	ONS only	Anthropometrics, energy and protein intake, QoL questionnaire	Higher caloric/proteir intake, QoL improvemen after hospitalization	Small sample, two intervention groups	13
Norman K 2008	Malnourished inpatients with GI disease	101	Dietary counseling with ONS over 3- month period		BMI, muscle strength readmission, QoL	Improved hand grip strength and peak flow fewer readmissions, better QoL	two intervention	14
Gariballa SA, 2007	Acutely il inpatients >65y	225	400 ml ONS/d	Standard nutritional care plus placebo	Nutritional status depression (geriatric depression questionnaire), cognitive function	Significant improvement in depression score after 6 month, no difference in cognitive function	High lost to follow number	15
Gariballa S 2006	Malnourished inpatients >65y	445	400 ml ONS/d	400 m placebo/d	Barthel's index readmissions, LOS mortality	Fewer readmissions otherwise no effect	Low adherence or intervention	16
Johansen N, 2004	Malnourished inpatients	212	Individualized nutritional therapy	Standard nutritional care	Caloric intake, LOS complications, mortality QoL	Higher caloric/proteir intake, shorter LOS	Small sample	17
Hickson M 2004	Malnourished medical inpatients, >65 y old	592	0 )	Standard nutritional care	Weight/BMI, Barthel's index, infection, LOS, inhospital mortality	Less antibiotic use otherwise no effect	Short training for health care assistants (15h)	18

BMI, body mass index; d, day(s); GI, gastro-intestinal; h, hours(s); LOS, length-of-stay; m, month(s); ONS, oral nutrition supplement; QoL, quality-of-life

#### 2.2. Risk benefit

Despite the absence of high-quality RCT data, the current consensus clinical approach in unselected medical inpatients is to provide nutritional therapy to reach nutritional requirements including caloric and protein targets, as well as micro-nutritional requirements. Importantly, some recent data from critical care suggested even harmful effects of aggressive early feeding, as well as glutamine supplementation which may be explained by different reasons. During the acute phase of illness, the body mobilizes substrates from muscle and fat tissue to match the increased resting energy expenditure. Exogenous calories then no longer inhibit gluconeogenesis. Excessive nutrition during the acute phase of illness can thus induce occult overfeeding. Still, recent critical care research from Switzerland reported benefit from individually optimized energy supplementation when patients were well selected. The contradictory findings from these trials may be partly explained by the differences in patient population, nutritional strategy and trial design. A key consideration which not only applies to critical care is therefore the fact that every ill patient is different, and nutritional strategies and goals need to be personalized and tailored to individual requirements.

Importantly, data from critical care cannot unconditionally be transferred to medical inpatients with a lower degree of disease severity. Still, the above-mentioned conflicting observations re-emphasize that nutritional therapy is a medical intervention with associated risks and costs, and call into question todays nutritional approach in medical inpatients. The current lack of strong guideline recommendations for type, caloric amount and timing of nutritional therapy in acutely-ill medical inpatients outside critical care is mainly explained by the paucity of high-level evidence showing such therapy's efficacy, safety and cost benefits, and the absence of knowledge regarding which patient population do or do not benefit. Hence, evaluation of efficacy, safety and possible cost benefits within a large, well-controlled conclusive RCT is warranted to assess the effects of early nutritional therapy on patient outcomes in the medical inpatient setting. The EFFORT trial will not only answer the question about overall benefit or harm, but using a physio-pathological mechanistic approach, it also will explore and provide conclusive answers about whether, why, how, and in which patient populations nutritional therapy does or does not works.

# 2.3. Choice of study population

Most current nutritional research has focused on selected medical diseases (e.g., pancreatitis). Consequently, these "clean" results may not be generalizable to "real-life" unselected medical inpatients with multiple comorbidities and illnesses. Comparative effectiveness research aims at improving quality, effectiveness, and efficiency of health care and at helping patients and healthcare professionals make informed decisions. To achieve these goals, research must address the patient population that actually consumes the most health care, specifically polymorbid, frail, elderly patients with complex combinations of medical diagnoses. Although accounting for the majority of costs, this patient population is the least

studied To correct this disparity, clinical trials should include large, representative populations, to enable examination of treatment effects within key subpopulations, and to allow robust head-to-head comparison of interventions.

EFFORT will close this important gap. The project focuses on a major issue in hospital care, namely, whether, how and why early nutritional therapy affects outcomes of unselected, elderly, frail acutely-ill medical inpatients. Evidence generated by this project will therefore easily be transferable to clinical practice and thus can be expected to exert a major direct impact on current patient management.

# 3. Objectives and purpose

# 3.1. Overall hypothesis

Our overall hypothesis states that in acutely-ill medical inpatients at risk for undernutrition, early nutritional therapy to reach nutritional targets is a cost-effective strategy to prevent mortality, morbidity and decline in functional outcomes. The alternative hypothesis is that early nutritional therapy has no beneficial effects, but increases the risk of complications, hospital LOS and overall treatment costs.

# 3.2. Objective

Our aim is to conduct a large investigator-initiated, non-commercial RCT to compare a "state-of-the-art" individualized nutritional therapy strategy to cover nutritional requirements based on pre-specified nutritional therapy guidelines (intervention group) versus a control group without nutritional therapy in a large representative medical inpatient population at risk for malnutrition.

# 3.3. Setting

Several secondary and tertiary Swiss hospitals have agreed to participate in this multicenter trial as active recruitment centers (i.e. University hospitals / Kantonsspitals in Aarau, Basel, Berne, Lucerne, Muri, Winterthur, Zofingen, Lausanne).

Additionally, we have two collaborating international sites in France and the United States, who will seek additional funding to join our efforts.

The Clinical Trial Unit (CTU) of the University of Basel will provide logistic and statistical support.

# 4. Design of the trial

# 4.1. Study design

This is an investigator-initiated, randomised controlled superiority trial with an open intervention comparing the effects of a nutritional intervention with a usual care control group.

# 4.2. Primary, secondary and safety endpoints

All patients will be assessed daily until hospital discharge and contacted after 30 and 180 days via telephone for a structured interview by blinded study nurses to assess primary and secondary endpoints.

The primary composite endpoint is combined adverse outcome within 30 days defined as

- (a) All-cause mortality
- (b) Admission to the intensive care unit from the medical ward
- (c) Unplanned hospital readmission
- (d) Major complications (defined according to previous trials) as a new occurrence (being diagnosed after inclusion into the trial) of
  - I. nosocomial infection or abscess requiring antibiotic treatment
  - II. respiratory failure with need for invasive or non-invasive ventilation (continuous positive airway pressure, CPAP)
  - III. major cardiovascular event (stroke, intracranial bleeding, cardiopulmonary arrest, myocardial infarction with and without invasive procedure) or pulmonary embolism
  - IV. acute renal failure (defined by 2x increase of baseline creatinine or new requirement of dialysis do to volume overload or electrolyte disturbance)
  - V. gastro-intestinal failure
- (e) decline in functional status of 10% or more from admission to day 30 measured by the Barthel's index (Appendix 1). This index measures performance in activities of daily living and comprises two groups of items, one related to self-care (feeding, grooming, bathing, dressing, bowel and bladder care, and toilet use), the other related to mobility (ambulation, transfers, and stair climbing). The resulting score ranges from 100 to 0 with lower scores indicating more severe disability. For the purpose of this study, a significant decrease in functional outcome will be defined as a decrease in Barthel's index by ≥10% from admission to day 30.

#### Secondary endpoints will be defined as follows:

- (a) each single component of the primary endpoint at day 30
- (b) each single component of the primary endpoint and the combined endpoint at short term, ie, at day 10 or hospital discharge whatever comes first
- (c) each single component of the primary endpoint and the combined endpoint at long term term, ie, at day 180
- (d) short-term nutritional and functional outcomes from inclusion to day 10 or hospital discharge (whatever comes first) including nutritional intake, improvement in muscle strength measured with handgrip strength, lean body mass, changes in undernutrition markers (pre-albumin, retinol-binding protein, body weight, BMI)];

- (e) hospital outcomes measured at hospital discharge defined as total hospital LOS, discharge home vs. post-acute care facility, new decubital ulcer;
- (f) Improvement in quality of life measured on admission and at 30-day and 180-day using the EuroQol Group 5-Dimension Self-Report Questionnaire (Appendix 3) and selected items from the Functional Assessment Anorexia-Cancer Therapy [FAACT] questionnaire),

Safety endpoints including side effects from nutritional therapy will be assessed daily until hospital discharge. A causal relationship with the trial will be rated by two study team members as unrelated / unlikely / possible / probable / definitely / not assessable. The following side effects were defined:

- a) Adverse gastrointestinal effects (diarrhea, nausea, vomiting, abdominal pain)
- b) Complications due to tube feeding or center catheter for parenteral nutrition,
- c) Refeeding syndrome,
- d) Liver or gall bladder dysfunction
- e) Hyperglycemia (defined as glucose levels >12mmol/l or persistent levels >10mmol/l in patients without diabetes or well controlled diabetes)

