#### 8.3. Sample Size considerations

This study is designed to show superiority of nutritional therapy compared to "appetite-guided" standard care regarding the composite primary endpoint. Our hypothesis is that early nutritional therapy will reduce mortality and morbidity within a follow up period of 30 days after the index hospitalization. From preliminary observational data collected during the TRIAGE pilot study, we estimate that 40% of the target patient population (NRS ≥3 points and LOS ≥5days) will reach the primary endpoint within 30 days (10% mortality, 5% ICU admission from the hospital ward, 15% complications, 10% functional decline with 10% reaching more than 1 endpoint). We hypothesize that our nutritional intervention will decrease this risk by an absolute number of 6% (relative decrease of 15%), i.e., from 40% to 34%. For a comparison of two independent binomial proportions using Pearson's Chi-square statistic with a Chi-square approximation with a two-sided significance level of 0.05, a sample size of 1'359 per group achieves a power of at least 0.9 when the proportions are 0.4 and 0.34.

Thus, a total number of 2000-3000 patients will provide the study with a power of 78-90% to detect a 15% relative decrease in the risk to reach the primary endpoint. The table below shows sample sizes for different assumptions regarding effectiveness of our intervention and power.

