# 13.2. Cost-effectiveness analysis of nutritional therapy

**Purpose:** to perform a cost-effectiveness calculation for early nutritional therapy in medical inpatients at risk for undernutrition including cost-effectiveness and cost-utility analyses. These analyses will be from the health-care payers' perspective using intervention data generated in the RCT.

**General approach:** The total cost calculation will include nutritional costs (including nutritional products and estimated time of dieticians spent with patients) and all medical costs within 30 days after study inclusion. The total cost calculation also will include all hospitalisations after index hospitalisation. We

will derive estimates of the real costs using REKOLE a comprehensive accounting algorithm used by Swiss hospitals to internally compute provider costs. Cost-effectiveness will be expressed as the incremental cost-effectiveness ratio. Non-parametric bootstrapping will be used to estimate 95%Cls for differences in incremental costs and effects. We will further calculate the probability value that nutritional therapy is cost-effective for a range of different willingness to pay values. We will define confidence intervals for the relevant cost difference. We will assume equivalence if the difference in total direct costs will lie between the equivalence margins. Non-inferiority of costs will be demonstrated if the upper limit of the confidence interval for cost differences between the two strategies will be smaller than the cost difference. In a second step we will perform a joint analysis of effects and costs in a cost-utility analysis by analysing the cost per quality adjusted life years (QALY) gained. We will present an overall analysis, and different subgroup analyses as defined in the RCT. Specifically, we will look at patients age (<60, 60-75, >75 years), gender, risk for undernutrition stratified according to initial NRS (3, 4, >4 points), main medical diagnosis (systemic infection, heart failure, acute renal failure, gastro-intestinal disease, tumor), comorbidities (diabetes, chronic renal failure), LOS (<8 days, ≥8 days) and BMI (<20, 20-25, >25-30, >30).

**Presentation of results:** To assess the shape of the joint sampling distribution of costs and effects we will present the joint density distribution of incremental costs and effects on the cost-effectiveness plane.

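### The short-term composite closes at discharge, so readmission cannot occur in it and its follow-up depends on length of stay; separately, the 30-day primary window needs one stated origin

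*Protocol*

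**What the plan says.** Protocol 4.2 lists secondary endpoint (b) as "each single component of the primary endpoint and the combined endpoint at short term, ie, at day 10 or hospital discharge whatever comes first". The components are those of the primary composite, and they include "Unplanned hospital readmission" and a "decline in functional status of 10% or more from admission to day 30 measured by the Barthel's index". Endpoint (e) in the same list covers "hospital outcomes measured at hospital discharge defined as total hospital LOS", so LOS is itself an outcome. Section 3.1 names a longer LOS as part of the alternative hypothesis. Section 6.2 states that patients and caregivers are not blinded.

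Section 8.2 plans to follow Barthel's index at admission, day 8 and day 30.

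The start of the 30-day period is worded differently in different places:
- 4.2: "The primary composite endpoint is combined adverse outcome within 30 days defined as", with no start given. The Barthel component runs from admission, and complications count if diagnosed after inclusion.
- 8.3: the hypothesis is that therapy "will reduce mortality and morbidity within a follow up period of 30 days after the index hospitalization".
- 13.2: the cost analysis takes "all medical costs within 30 days after study inclusion".

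**The concern.** A window that ends at discharge has a length decided after randomisation. If one arm goes home earlier, it is watched for less time and will tend to show fewer short-term events even when the daily risk is the same; if it stays longer, it will tend to show more. The protocol gives reasons to expect that LOS could differ: section 3.1 allows an increase, Table 1 lists earlier trials of individualised counselling or therapy with shorter stays, and the unblinded care team influences discharge.

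The same rule makes one promised comparison empty, because nobody can be readmitted before being discharged. At stake is how endpoint (b) can be interpreted: a between-arm difference in it could not be separated from a difference in LOS.

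The second matter is smaller. If the 8.3 phrase were taken as the endpoint definition, the primary window would last LOS plus 30 days and would also depend on LOS. The text has to exclude that reading.

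**Working it through.** **1. The plan's own figure.** Section 8.3 gives 1,359 per group for 0.40 versus 0.34, two-sided alpha 0.05, power 0.9. With the pooled-variance chi-square formula,

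n = [1.960·√(2·0.37·0.63) + 1.2816·√(0.40·0.60 + 0.34·0.66)]² / 0.06² = (1.338 + 0.873)² / 0.0036 ≈ 1,359.

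It reproduces. The calculation concerns the primary endpoint, and nothing below changes it as long as the 40% refers to a fixed 30-day window.

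**2. Readmission in endpoint (b).** Time of readmission > time of discharge ≥ end of window, where the window ends at min(discharge, day 10). The count is therefore zero in each arm. No assumption is needed.

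**3. Effect of LOS on the short-term window.** The protocol gives no LOS distribution, so the inputs here are assumptions: log-normal LOS, and the same constant daily hazard in both arms (no treatment effect). The window is W = min(LOS, 10). Simulation used 2,000,000 stays, and the shifted stay was LOS − 1 with a floor of 1 day.

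| Median LOS (days) | log SD | mean W | mean W, 1 day shorter | change |
|---|---|---|---|---|
| 6 | 0.4 | 6.27 | 5.35 | −14.6% |
| 6 | 0.8 | 6.22 | 5.51 | −11.4% |
| 8 | 0.6 | 7.48 | 6.81 | −9.0% |
| 10 | 0.4 | 8.74 | 8.19 | −6.3% |
| 10 | 0.8 | 7.92 | 7.41 | −6.5% |

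For median 8 and log SD 0.6, a stay 10% shorter gives a mean W of 7.05 (−5.7%). With a constant low hazard, expected events fall roughly in proportion to W. A longer stay moves the figure the other way.

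**4. Same question with another LOS shape.** Assumptions: gamma LOS (shape 2.5), control mean 8 or 10 days, constant hazard equivalent to 20 to 40% risk by day 30, no treatment effect, 1,000 to 1,500 per arm, nominal two-sided 5% test.

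| LOS difference | apparent risk ratio | rejection rate |
|---|---|---|
| 0.5 day | 0.96 to 0.98 | 5 to 6% |
| 1 day | 0.92 to 0.95 | 6 to 12% |
| 2 days | 0.83 to 0.90 | 9 to 38% |

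**5. What a LOS + 30 reading would do to the primary endpoint.** Hypothetical only. Take hazard h = −ln(1 − 0.40)/30 = 0.0170 per day.
- LOS 10: 1 − exp(−40h) = 49.4%.
- LOS 8: 1 − exp(−38h) = 47.6%.

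A two-day LOS difference alone would give about 1.75 points, against the planned 6.

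**6. The anchors side by side.** Admission (Barthel component, 4.2), inclusion (complications in 4.2, costs in 13.2) and the index hospitalisation (8.3) are three wordings. Section 5.1 allows inclusion within 24 to 48 hours of admission, so the first two nearly coincide. The third stands apart only if it is read as starting at discharge.

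**The case against.** **Importance of (b).** It is one secondary endpoint. The same components and the composite are also analysed at days 30 and 180, and no main conclusion rests on (b). It can be read as an in-hospital outcome capped at day 10, and a component that is zero in both arms creates no bias between arms. This stands as a limit on importance. It does not remove the dependence on LOS for the remaining components, and the protocol does not label (b) as in-hospital.

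**Size.** The LOS distribution and the constant hazard are assumed. Patients sent home early are probably the more stable ones, so the days lost after discharge may carry few events; events may also prolong the stay. A half-day difference hardly matters. This stands: the 6 to 15% is an illustration and may be too high.

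**Direction.** A reader might infer a bias in favour of the intervention. The documents do not support that: section 3.1 allows LOS to rise, and the distortion would then run against it.

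**Functional decline.** A reader might infer that this component is undefined early and should leave the short-term composite. Section 8.2 already plans a Barthel reading at day 8, and (b) re-times the components just as (c) does for day 180. What is missing is only which early reading counts.

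**Primary window.** A reader might infer from 8.3 that the primary endpoint is counted from discharge. The phrase stands in a hypothesis sentence, the next sentence says only that 40% reach the endpoint within 30 days, and the definition in 4.2 does not mention discharge. The cost wording in 13.2 fits an inclusion origin.

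**Conclusion.** The point holds for the short-term secondary endpoint (b) only. That readmission cannot occur in its window follows from the text alone, and so does the dependence of follow-up on LOS. The size does not: a one-day difference changes the mean window by about 6 to 15% under log-normal LOS with median 6 to 10 days, log SD 0.4 to 0.8 and constant hazard. It would be less if hazard is lower after discharge, and either sign is possible.

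For the primary endpoint there is an inconsistency of wording across 4.2, 8.3 and 13.2, and no proof of a discharge-anchored analysis. The sample size does not change if the 40% refers to 30 days from a fixed origin; the protocol should confirm that it does.

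**What to change.** **Endpoint (b).** Count short-term events from randomisation to a fixed day 10, whether or not the patient has been discharged, using chart dates and event dates asked for in the day-30 interview already planned. Readmission then becomes observable. The cost is wording plus a few date fields. The small downside is that some post-discharge dates will be recalled by telephone, and the share obtained this way will itself vary with LOS.

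Alternatively, keep the present window, label (b) as an in-hospital outcome capped at day 10, and remove readmission from it. This costs wording only, but the dependence on LOS remains and should be stated when the result is interpreted.

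In either case, keep functional decline and state which early Barthel reading defines it (8.2 lists day 8), including what applies to patients discharged before that reading.

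**Primary window.** In the synopsis, 4.2 and 8.3, state that the 30 days run from randomisation. Use the same origin for the day-30 call and for the costs in 13.2, and confirm that the 40% event rate was estimated for that window. This is a change of wording.
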